#### 5.7.3. ANGIOEDEMA QUALITY OF LIFE (AE-QOL) QUESTIONNAIRE

The Angioedema Quality of Life (AE-QoL) is a questionnaire on the quality of life of patients suffering from recurrent angioedema. It consists of 17 specific questions that are associated with work, physical activity, free time, social relations, and diet. Each question is then answered with Never, Rarely, Occasionally, Often and Very Often, which will be scored as 1, 2, 3, 4 and 5 respectively. The 17 questions will be grouped into four categories as follow, and a total score will also be calculated:

- Functioning
  - o 1. Impairment of work
  - o 2. Impairment of physical activity
  - o 3. Impairment of spare time activities
  - o 4. Impairment of social relations
- Fatigue/Mood
  - o 6. Difficulties of falling asleep
  - o 7. Waking up during the night
  - o 8. Feeling tired during the day
  - o 9. Difficulties in concentrating
  - o 10. Feeling downhearted
- Fears/Shame
  - o 12. Feeling burden at having swellings
  - 13. Fear of new suddenly appearing swellings
  - 14. Fear of increased frequency of swellings
  - 15. Ashamed to visit public places

Document: \SW20RND01\VistaTempDir\Temp28232\Shire\_0624\_209\_SAP\_v1 0.docx
Author: Version Number:

Version Date:

Version Number: 1.0
Version Date: 21Jul2017

Template No: CS TP BS016 Revision 4 Reference: CS WI BS005

PROTOCOL: 0624-209 Page 19 of 35

1.0

Reference: CS\_WI\_BS005

- 16. Embarrassed by the appearance of swellings
- 17. Fear of long-term negative drug effects
- Nutrition
  - 5. General limitations in foods and eating 0
  - 11. Limitations in the selection of food or beverages?
- **Total Score** 
  - Question 1 to Question 17

\\SW20RND01\\VistaTempDir\Temp28232\\Shire\_0624\_209\_SAP\_v1 0.docx PPD Version Number: Document: Author:

Version Date: 21Jul2017

Template No: CS\_TP\_BS016 Revision 4 Effective Date: 01Apr2016

Summary and change from baseline for the total score will be presented for all visits.

#### 5.7.4. SENSITIVITY ANALYSIS

The following sensitivity analyses will be performed for efficacy analysis on NNA described in Section 5.7.1.

The first sensitivity analysis includes only subjects with treatment compliance. The definition of treatment compliance will be given in Section 5.8.8. That is, only subjects who have no dose interruption and receive 24 complete infusions are included in the analysis.

In the second sensitivity analysis, all FAS subjects will be included in this sensitivity analysis, however data will only include up to the point when non-treatment compliance occurred.

#### 5.8. ANALYSIS OF SAFETY

#### 5.8.1. ADVERSE EVENTS

Adverse Events (AEs) will be coded using Medical Dictionary for Regulatory Activities (MedDRA) central coding dictionary version 19.0. Events will be classified by system organ class (SOC) and preferred term (PT). Only treatment emergent adverse events (TEAEs) will be summarized.

Treatment-emergent events include all AEs that start during the treatment period and were not seen at baseline, or were seen at baseline but worsened in frequency and/or severity during the treatment period.

The incidence of injection site reaction AEs will also be summarized at PT and SOC level. Injection site reaction AEs are any PT that include the term 'injection site reaction'.

The incidence of TEAEs will be summarized by intensity ('Mild', 'Moderate' or 'Severe') at PT and SOC level. For each subject and PT, only the most severe AE will be counted.

The incidence of AEs related to study drug will be summarized at PT and SOC level. Events with a relationship to study drug classified as 'Possibly Related', 'Probably Related', and 'Definitely Related' will be categorized as 'Related'. If a subject experiences the same event (at PT level) on more than one occasion, then only one event will be counted, and this event will be categorized as 'Related' if any of the events under that PTs are categorized as 'Related'.

The incidence of AE by PT, the incidence of serious AE by PT and SOC, and the incidence of serious AE by PT will also be presented.

Adverse events will be sorted by SOC in alphabetical order, then within SOC, sort PT in descending frequency.

All AEs for each subject, including the same event on several occasions will be listed, giving both preferred term and the original term used by the investigator. Serious AEs will be presented separately on an additional listing.

Document: \\SW20RND01\VistaTempDir\Temp28232\Shire\_0624\_209\_SAP\_v1 0.docx

Author: PPD Version Number: 1.0
Version Date: 21Jul2017

Template No: CS TP BS016 Revision 4 Reference: CS WI BS005

PROTOCOL: 0624-209 Page 21 of 35

1.0

21Jul2017

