|---|---------|----------------------------------|----------------|----------------|----------------|----------------|----------------|------------------|---|----------------|----|----|----|----------------|----|----------------|----|----------------|----|----------------|----|----------------|----|----------------|
| | 1 | 1 2 | | 2 | 3 | | 4 | | 5 | | 6 | | 7 | | 8 | | 9 | | 10 | | 11 | | 12 | |
| | | DOSING VISITS (1 to 24) | | | | | | | | | | | | | | - | | | | | | | | |
| Procedure | 1 | 2 | 3 | 4 | 5 | 6 | 7 | 8 | 9 | 10 | 11 | 12 | 13 | 14 | 15 | 16 | 17 | 18 | 19 | 20 | 21 | 22 | 23 | 24 |
| Investigational product admi | nistra | tion ^a | | | | | | | | | | | | | | | | | | | | | | |
| Study site visits | X^{b} | Xb | Xc | Xc | X^{c} | X ^c | X^{c} | $X^{c,d}$ | | | | | | | | X^{f} | | | | | | | | X^{f} |
| Optional at home visits | | | | | | | | | X | Xe | Xe | Xe | Xe | Xe | Xe | | Xe | Xe | Xe | Xe | Xe | Xe | Xe | |
| Follow-up contact | | | | | | | | | | X ^g | | Xg | | X ^g | | | | X ^g | | X ^g | | X ^g | | |
| Training at the study site ass | ociate | d witl | n self- | admin | istrat | ion | | | | | | | | | | | | | | | | | | |
| Investigator or qualified delegate instruct subjects | X^b | X ^b | | | | | | | | | | | | | | | | | | | | | | |
| Subject self-administration with supervision ^f | | | X ^c | X ^{c,d} | | | | | | | | X ^f | | | | | | | | X ^f |

- a: Subjects will receive study drug twice weekly (every 3 or 4 days) during the 12-week treatment period (Dosing Visits 1-24). Study drug will be administered to all subjects at the investigational site for Dosing Visits 1 through 8, 16, and 24. Other doses of study drug may be administered at the investigational site or at the subject's home. Subjects (at least 12 years of age or their caregivers) considered suitable candidates (ie, those with a physical and mental capability of learning, adequate venous access, and willing to be trained) will be allowed to self-administer one or more doses of study drug after receiving detailed training by the Investigator or qualified delegate (see Section 5.3.1) and having demonstrated the necessary skills. Doses of CINRYZE that are self-administered will be entered as such in the CRF.
- b: Investigator or qualified delegate will administer the first 2 doses of investigational product while instructing the subject on the process.

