6.2 Adverse Event Collection

At each study visit, subjects will be questioned in a general way to ascertain if AEs have occurred since the previous visit (eg, "Have you had any health problems since your last visit?"). Adverse events will be collected from the time informed consent is signed through 7 days after the last dose of investigational product. This includes events occurring during the screening phase of the study, regardless of whether or not the investigational product is administered. In addition, the investigator will report all SAEs that occur through 30 days after the last dose of investigational product to PAREXEL International Pharmacovigilance and the respective Independent Reviewing Authority according to local reporting requirements.

Please refer to Section 9, Adverse and Serious Adverse Events Assessment.

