7.4 Safety Analyses

The following will be assessed:

- Adverse events (including treatment-emergent adverse events).
- Summary statistics and changes from baseline to post-baseline for laboratory testing, vital signs, and, if applicable, any ECG findings will be presented.
- Results of C1 INH antibody testing will be reported for individual subjects and summarized as appropriate.

NOTE: Treatment-emergent events include all adverse events that start during the treatment period (and up to 7 days after the last dose of investigational product) and were not seen at baseline, or were seen at baseline but worsened in frequency and/or severity during the treatment period (and up to 7 days after the last dose of investigational product).

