#### 5.7.2. TREATMENT OF BREAKTHROUGH ANGIOEDEMA ATTACKS

A breakthrough attack is defined as an angioedema attack that occurs during long-term prevention therapy with CINRYZE® (i.e, between first study drug and last study drug dose).

The following efficacy endpoints for treatment of breakthrough angioedema attacks will be assessed by CINRYZE® treated attacks, non-CINRYZE® C1-INH treated attacks and all other attacks (including any medications other than C1-INH and untreated attacks):

- The number of subjects with breakthrough angioedema attacks.
- The number of subjects with 1, 2, 3 or more angioedema attacks.
- The number of subjects who achieve initial improvement and Complete Resolution.
- Time to initial improvement and time to Complete Resolution.

Additional analysis for breakthrough angioedema attacks treated with CINRYZE® will also be presented for:

- The number of subjects with breakthrough angioedema attacks.
- The number of subjects with 1, 2, 3 or more angioedema attacks.
- Time from onset of attack to time treated by CINRYZE.
- The number of subjects who achieve initial improvement and Complete Resolution. Complete Resolution is defined as the cessation of all symptoms of the breakthrough angioedema attack since onset of attack.
- Time from the start of study drug administration, CINRYZE°, for the particular attack to the time of initial improvement and time to Complete Resolution.

\\SW20RND01\\VistaTempDir\Temp28232\Shire\_0624\_209\_SAP\_v1 0.docx Document: Version Number:

Version Date: 21Jul2017

Template No: CS\_TP\_BS016 Revision 4

Effective Date: 01Apr2016

Author:

Copyright © 2009, 2010, 2012, 2016 Quintiles Transnational Corp. All rights reserved.

The contents of this document are confidential and proprietary to Quintiles Transnational Corp. Unauthorized use, disclosure or reproduction is strictly prohibited.

Shire
PROTOCOL: 0624-209
Page 18 of 35

Derivations will be constructed as follow:

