#### 5.8.8. TREATMENT COMPLIANCE

Treatment compliance is defined by 24 complete infusions, and no dose interruption. Dose interruption means that the gap between any two consecutive doses is at least 6 days.

The compliance for subjects who have no dose interruption or subjects whose treatment duration is less than 12 weeks (84 days) is calculated as:

$$(\%) = \frac{(}{}$$
 x100

The compliance for subjects who have dose interruption and the treatment duration is greater than 12 weeks (84 days) is calculated as:

where 3.5 is the average number of days between 2 infusions in one week.

Document: \\SW20RND01\\VistaTempDir\Temp28232\\Shire\_0624\_209\_SAP\_v1 0.docx

Author: PPD Version Number: 1.0
Version Date: 21Jul2017

Template No: CS TP BS016 Revision 4 Reference: CS WI BS005

PROTOCOL: 0624-209 Page 25 of 35

1.0

Reference: CS\_WI\_BS005

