#### 6.2. CHANGES FROM THE ANALYSES PLANNED IN THE PROTOCOL

Due to insufficient data collection, the analysis of clinical relief has not been conducted as planned.

\\SW20RND01\\VistaTempDir\Temp28232\\Shire\_0624\_209\_SAP\_v1 0.docx PPD Version Number: Document: Author:

Version Date: Reference: CS\_WI\_BS005

Template No: CS\_TP\_BS016 Revision 4

Effective Date: 01Apr2016

Copyright © 2009, 2010, 2012, 2016 Quintiles Transnational Corp. All rights reserved.

Shire
PROTOCOL: 0624-209
Page 27 of 35

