## **ALGORITHM FOR TREATMENT EMERGENCE OF ADVERSE EVENTS**

START DATE	STOP DATE	ACTION	
Known	Known	If start date < study med start date, then not TEAE	
		If start date >= study med start date, then TEAE	
	Partial	If start date < study med start date, then not TEAE	
		If start date >= study med start date, then TEAE	
	Missing	If start date < study med start date, then not TEAE	
		If start date >= study med start date, then TEAE	
Partial, but known components show that it cannot be on or after study med start date	Known	Not TEAE	
	Partial	Not TEAE	
	Missing	Not TEAE	
Partial, could be on or	Known	If stop date < study med start date, then not TEAE	
after study med start date		If stop date >= study med start date, then TEAE	
	Partial	Impute stop date as latest possible date (i.e. last day of month if day unknown or 31st December if day and month are unknown), then:	
		If stop date < study med start date, then not TEAE	
		If stop date >= study med start date, then TEAE	
	Missing	Assumed TEAE	

\\SW20RND01\\VistaTempDir\Temp28232\\Shire\_0624\_209\_SAP\_v1 0.docx PPD \qquad \text{Version Number:} Document:

Author: 1.0 Version Date: 21Jul2017

Template No: CS\_TP\_BS016 Revision 4 Effective Date: 01Apr2016 Reference: CS\_WI\_BS005

Shire
PROTOCOL: 0624-209
Page 34 of 35

START DATE	STOP DATE	ACTION
Missing	Known	If stop date < study med start date, then not TEAE  If stop date >= study med start date, then TEAE
	Partial	Impute stop date as latest possible date (i.e. last day of month if day unknown or 31st December if day and month are unknown), then:
		If stop date < study med start date, then not TEAE
		If stop date >= study med start date, then TEAE
	Missing	Assumed TEAE

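### SAP 5.8.1 and SAP Appendix III classify treatment-emergent AEs differently, neither matches protocol 7.4, and the local-reaction search string cannot find infusion-site terms

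*SAP*

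**What the plan says.** Three rules for treatment emergence are in force.

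- Protocol 7.4: "Treatment-emergent events include all adverse events that start during the treatment period (and up to 7 days after the last dose of investigational product"), provided they are new since baseline. Events present at baseline count if they worsened within the same extended window.
- SAP 5.8.1: "Treatment-emergent events include all AEs that start during the treatment period and were not seen at baseline", or worsened during that period. Both seven-day extensions, for onset and for worsening, are gone.
- SAP Appendix III, algorithm for treatment emergence: "If start date >= study med start date, then TEAE". The table starts with the case where start and stop dates are both known, so it classifies every AE and not only those with incomplete dates. It has no end date and no baseline test.

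SAP 6.2 lists one departure from the protocol: "Due to insufficient data collection, the analysis of clinical relief has not been conducted as planned". The treatment-emergence rule is not mentioned. SAP section 1 presents the document as an elaboration of protocol Amendment 5, which contains the seven-day wording.

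SAP 5.8.1 restricts summaries to treatment-emergent events and lists all AEs by subject. It also promises a summary of local reactions, found by preferred terms (PTs) containing 'injection site reaction'. The product is given by IV infusion (protocol 5.3), and protocol 1.1.2 describes local events in earlier studies as infusion site pain, bruising and rash.

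**The concern.** Safety and tolerability is the first-listed objective. Because only treatment-emergent events are tabulated, the classification rule decides what a reader of the AE tables sees. Two programmers working from the same SAP could produce different tables, and neither set would follow the protocol.

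The errors run in opposite directions. The 5.8.1 text leaves out events that the protocol counts and that sites are told to collect: "Adverse events will be collected from the time informed consent is signed through 7 days after the last dose of investigational product". Appendix III counts events that the protocol excludes. The search string is a separate and smaller fault: the local-reaction summary could show no events although infusion-site reactions occurred.

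**Working it through.** There is no power or sample-size figure to reproduce; the check applies the three rules to the same events.

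**Inputs.** Non-serious AEs are collected to 7 days after the last dose (protocol 6.2). SAEs are collected to 30 days, and related SAEs later still (protocol 9.2.4; Schedule 3, footnote e). Worsening of a pre-treatment event is recorded as a new AE with its own onset date (protocol 9.1.1).

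**End of the treatment period.** The SAP does not define it for AEs. Protocol Schedule 2, footnote a, ties it to the dosing visits: "during the 12-week treatment period (Dosing Visits 1-24"). SAP 5.7.2 gives the on-treatment span for attacks as "between first study drug and last study drug dose". Protocol 7.4 adds the seven days in brackets, so its own treatment period does not already contain them. I therefore take the last dose as the end.

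**Classification** (days are counted from the last dose):

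| Event | Protocol 7.4 | SAP 5.8.1 | SAP Appendix III |
|---|---|---|---|
| New AE, first to last dose | yes | yes | yes |
| Baseline event that worsens on treatment | yes | yes | yes |
| New or worsened AE, days 1 to 7 | yes | **no** | yes |
| SAE, days 8 to 30 | no | no | **yes** |
| Related SAE after day 30 | no | no | **yes** |
| Baseline event that restarts on treatment unworsened, if recorded as an AE | no | no | **yes** |

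Bold marks a departure from the protocol. SAP 5.8.1 departs in one row and Appendix III in three; the two SAP rules disagree in all four of those rows.

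**Tables affected.** The AE tables in SAP Appendix I are 14.3.1.1, 14.3.1.2.1, 14.3.1.2.2, 14.3.1.3.1, 14.3.1.3.2, 14.3.2.1 and 14.3.2.2. That is 7, and all are restricted to treatment-emergent events.

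**Size per subject.** One reclassified subject changes an incidence by 100/n percentage points, where n is the number treated. The SAP does not give n. The target is at least 6 completers, so if it is met n is at least 6 and the shift is at most 100/6 = 16.7 points. With 8 treated (illustrative) it would be 100/8 = 12.5. The documents give no event rate for the window, so an expected number of misclassified events cannot be derived.

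**Search string.** I tested it as a case-insensitive substring on seven example terms built from the protocol's wording: infusion site pain, bruising, rash and reaction, and injection site pain, bruising and reaction. It matches 0 of the 4 infusion-site terms and 1 of the 3 injection-site terms, so 1 of 7. A search on either site phrase matches 7 of 7. The examples are assumptions, not coded data. No table title in Appendix I names the local-reaction summary.

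**Supplemental doses.** Protocol 6.12.1 allows a supplemental dose through one week post-treatment. If such a dose counts as the last dose, the protocol window could end about 7 + 7 = 14 days after the last scheduled dose instead of 7. Protocol 7.4 does not say which applies.

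**The case against.** The strongest reply is that the practical effect is narrow. Appendix III is the only step-by-step flagging rule in the SAP, so it is probably the one that would be programmed. Under it no non-serious AE in the seven days is lost, because collection of such events stops at day 7, and its late excess is confined to SAEs. Every AE is listed by subject, serious AEs have their own planned listing (16.2.7.2), and the study is small and descriptive. All of this stands. It limits the damage to the summary tables but does not say which rule governs, and it leaves the missing baseline test in Appendix III untouched.

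Stronger readings are tempting, and the documents do not support them.

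- A reader might infer that the window was shortened on purpose to keep late events out of view. Nothing shows intent. Given that the SAP says it elaborates Amendment 5, dropped wording is at least as plausible, and the listings keep the events visible.
- A reader might infer a treatment period ending at day 84, and so a different number of lost days, from the phrase in SAP 5.8.8, "whose treatment duration is less than 12 weeks (84 days"). That passage only selects a compliance formula. It also provides for treatment beyond 84 days, and protocol 5.5.2 lets interrupted subjects resume to complete 24 doses. A day-84 end would exclude AEs while such subjects were still being dosed.
- A reader might infer that infusion-site reactions would vanish from the tables. They would still appear in the general treatment-emergent tables. Whether the string misses any actual event depends on MedDRA coding, which the documents do not show. The absence of a local-reaction table is judged from titles only.

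The supplemental-dose question is an ambiguity in the protocol itself, not a conflict between protocol and SAP. It belongs here only because copying the protocol's wording would not by itself give one end date.

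**Conclusion.** The point holds and should be fixed. SAP 5.8.1 and SAP Appendix III contradict each other, neither reproduces protocol 7.4, and SAP 6.2 does not declare a change. With the treatment period taken to end at the last dose, following 5.8.1 removes seven days of collected events from all seven AE tables. Following Appendix III over-counts instead, by late SAEs and by unworsened recurrences of baseline events. These are alternatives, not errors that add up. The 16.7-point figure is for one subject with six treated, which is an assumption.

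The search string is wrong as written for an infused product, but its effect is confined to the local-reaction summary.

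**What to change.** - Put the full protocol 7.4 rule in both SAP 5.8.1 and Appendix III: onset from first dose to seven days after the last dose, and either absent at baseline or worsened from baseline. An end date alone would not bring Appendix III into line; it needs the baseline condition too. If another window is intended, declare and justify it in SAP 6.2.
- State whether a supplemental CINRYZE dose counts as the last dose for this analysis window.
- Flag SAEs that start after the window in the SAE listing already planned.
- Replace the search string with a prespecified list of infusion-site and injection-site PTs, and add the matching table to Appendix I.

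The cost is SAP wording, two conditions in the flagging program, one flag, one term list and one table. No new data are needed. The local-reaction count may rise, and treatment-emergent counts may be slightly higher than under the 5.8.1 text.

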#### 5.8.2. **CLINICAL LABORATORY EVALUATION**

Laboratory values will be obtained for hematology, clinical chemistry, coagulation, virology and urinalysis at the time points specified in Schedule 1 and Schedule 3 of the protocol. The laboratory tests will be performed by a central laboratory.

Descriptive statistics will be provided hematology, clinical chemistry and coagulation data at time points specified in Schedule 1 and Schedule 3 of the protocol. Descriptive statistics for change from baseline to post-baseline, and shifts with respect to normal ranges for the same period will also be presented. Data listings will be provided for all subjects. Laboratory values outside the normal range will be flagged.

Baseline is denoted as Visit 1.

Number of subjects with potentially clinically important (PCI) lab values will also be presented. Potentially clinically important lab values are defined as per Table 1 below.

\\SW20RND01\VistaTempDir\Temp28232\Shire\_0624\_209\_SAP\_v1 0.docx Document: Version Number: Author:

Reference: CS\_WI\_BS005

Version Date:

Template No: CS\_TP\_BS016 Revision 4

1.0

Table 1: Potentially important lab values

Test Item	Unit	Reference range	Criterion *1
WDC (11 B)	/micro L	2222 2222	> 15000
WBC (blood)		3300 - 9000	< 2000
Eosinophils (rel)	%	0.0 - 8.0	> 10.0
N	/micro L	(NT/A)	> 11000
Neutrophils (abs)		(N/A)	< 1000
Lymphocytes (abs)	/micro L	(N/A)	> 20000
Lymphocytes (abs)		(IV/A)	< 500
	g/dL	M: 13.5 - 17.5	>(BL) + 4.0
hemoglobin (blood)		F: 11.5 - 15.0	· (DL) · 4.0
		11110 1510	<(BL) – 3.0
platelet count	x10^4	14.0 - 34.0	> 60.0
	/micro L		< 10.0
aPTT-second	sec	25.0 - 36.0	> 90.0
PT-INR	(N/A)	0.85 - 1.15	> 2.875
BUN	mg/dL	8 - 23	> (BL) x 2.0
creatinine	mg/dL	M: 0.61 - 1.04 F: 0.47 - 0.79	> (BL) x 2.0
1 ( )	mg/dL	70 100	> 250
glucose (serum)		70 - 109	< 40
1.	mEq/L	127 147	> 155
sodium		137 - 147	< 130
	mEq/L	25.50	> 6.0
potassium		3.5 - 5.0	< 3.0
AST	U/L	10 - 40	> 200
ALT	U/L	5 – 45	> 225
ALP	U/L	100 - 325	> 1625
CPK	U/L	M: 60 - 270	M: > 1350
CPK		F: 40 - 150	F: > 750
total bilirubin	mg/dL	0.2 - 1.2	> 3.6
calcium	mg/dL	8.4 - 10.4	> 12.5
calcium		8.4 - 10.4	< 7.0
phosphorus	mg/dL	2.5 - 4.5	< 2.0

\*1 BL (Baseline) is Visit 1. When the sample is not collected at Visit 1, the alarm for variation (ratio/difference) is not performed.

\\SW20RND01\\VistaTempDir\Temp28232\\Shire\_0624\_209\_SAP\_v1 0.docx Version Number: Document: Author:

Version Date: 21Jul2017 Reference: CS\_WI\_BS005

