| Vital signs (BP, pulse) d, | X | X | X | | X | | X | | X | | X | | X | | X | | X | | X | | X | | X | | X |
| 12-lead ECG d | X | | | | | | | | | | | | | | | | | | | | | | | | |
| Hematology and clinical chemistry ^c | X | X | | | | | | | X | | | | | | | | X | | | | | | | | X |
| Urinalysis with microscopy ^c | X | | | | | | | | X | | | | | | | | X | | | | | | | | X |
| Coagulation (PT, aPTT, INR) ° | X | | | | | | | | X | | | | | | | | X | | | | | | | | X |
| Virology screening f | X | | | | | | | | | | | | | | | | | | | | | | | | |
| Pregnancy testing c, g | X | X | | | | | | | | | | | | | | | | | | | | | | | X |
| Study drug administration | | | | Ш | | Ш | | | 1 | Ш | | | See | Sched | lule 2 | | 1 | Ш | | | | | ı | ı | |
| Daily angioedema attack | | | | | | | | | | | | | | | | | | | | | | | | | |
| monitoring and study | | Х- | | | | | | | | | | | | | | | | | | | | | | —X | |
| diary h | | | | | | | | | | | | | | | | | | | | | | | | | |
| Adverse events | X i | Χ- | | | | | | | | | | | | | | | | | | | | | | — Х | |
| Immunogenicity (C1 INH antibody) ^c | | X | | | | | | | X | | | | | | | | X | | | | | | | | X |
| Quality of life | | 37 | | | | | | | 37 | | | | | | | | 37 | | | | | | | | 37 |
| questionnaire (AE-QoL) c | | X | | | | | | | X | | | | | | | | X | | | | | L | | | X |
| Self-administration survey | | | | | | | | | | | | | | | | | | | | | | | | | X |
| PK/PD assessments | | | X | | | | | | | | | | See | Sched | lule 4 | | | | | | | | | | X |

Protocol 0624-209 with Amendments 1, 2, 3, 4, and 5 CINRYZE (C1 inhibitor [human])

Schedule 1: Clinical Study Assessments – Screening and Treatment Period

| | | | TREATMENT PERIOD (BY STUDY WEEK) | | | | | | | | | | | | | | | | | | | | | | |
|-----------|-----------|---|----------------------------------|---|---|---|---|---|---|---|----|----|----|----|----|----|----|----|----|----|----|----|----|----|----|
| | | | 1 | | 2 | 3 | 3 | 4 | 1 | | 5 | (| 6 | | 7 | 8 | 8 | , | 9 | 1 | 0 | 1 | 1 | 1 | 2 |
| | Screening | | DOSING VISITS (1 to 24) | | | | | | | | | | | | | | | | | | | | | | |
| Procedure | a | 1 | 2 | 3 | 4 | 5 | 6 | 7 | 8 | 9 | 10 | 11 | 12 | 13 | 14 | 15 | 16 | 17 | 18 | 19 | 20 | 21 | 22 | 23 | 24 |

Page 24

30 Aug 2016

AE-QoL=angioedema quality of life; aPTT=activated partial thromboplastin time; BP=blood pressure; C1 INH=C1 inhibitor; ECG=electrocardiogram; INR=international normalized ratio; PD=pharmacodynamics: PK=pharmacokinetics: PT=prothrombin time

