6 STUDY PROCEDURES

Subjects meeting the eligibility criteria listed in Section 4 may be enrolled in the study after the nature and purpose of the protocol have been explained and written informed consent to participate has been voluntarily granted by the subject or permission for minors has been granted by a parent/legal guardian and assent has been provided by appropriate subjects (Section 14). For subjects who are screened (ie, those with signed written informed consent) but not enrolled, demographic information and reason for screen failure will be recorded in the CRF. Schedule 1, Schedule 2, and Schedule 3 provide details of study procedures and clinical assessments, and Schedule 4 provides timing of PK/PD blood sampling.

NOTE: It is possible for the Screening Visit and Dosing Visit 1 to occur on the same day. If this occurs—to prevent repetition of protocol procedures and avoid duplicate blood draws on the same day—following Screening procedures, only the following Dosing Visit 1 procedures will be performed:

- Concomitant medications
- Vital signs relative to study drug administration
- Study drug administration
- Daily angioedema attack monitoring and study diary
- Adverse event monitoring
- PK/PD and immunogenicity (C1 INH antibody) blood sampling
- Quality of life questionnaire

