9.1.5 Clinical Laboratory and Other Safety Endpoints

A change in the value of a clinical laboratory, vital sign, or ECG assessment can represent an AE if the change is clinically relevant or if, during treatment with the investigational product, a shift of a parameter is observed from a normal value to an abnormal value, or a further worsening of an already abnormal value. When evaluating such changes, the extent of deviation from the reference range, the duration until return to the reference range, either while continuing treatment

Protocol 0624-209 with Amendments 1, 2, 3 CINRYZE (C1 inhibitor [human])

or after the end of treatment with the investigational product, and the range of variation of the respective parameter within its reference range, must be taken into consideration.

If, at the end of the treatment phase, there are abnormal clinical laboratory, vital sign, or ECG values which were not present at the pre-treatment value observed closest to the start of study treatment, further investigations should be performed until the values return to within the reference range or until a plausible explanation (eg, concomitant disease) is found for the abnormal values.

The Investigator should decide, based on the above criteria and the clinical condition of a subject, whether a change in a clinical laboratory, vital sign, or ECG parameter is clinically significant and therefore represents an AE.

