Table 14.3.1.3.2 Serious Treatment-emergent Adverse Events by Preferred Term (Intent-to-Treat Safety Analysis Set

Table 14.3.2.1 Treatment-emergent Adverse Events by Maximum Severity, System Organ Class and Preferred Term (Intent-to-Treat Safety Analysis Set)

Table 14.3.2.2 Treatment-emergent Adverse Events Considered Related to Investigational Product by System Organ Class and Preferred Term (Intent-to-Treat Safety Analysis Set)

Table 14.3.4.1 Quantitative Clinical Laboratory Results: Hematology (Intent-to-Treat Safety Analysis Set)

Table 14.3.4.2 Quantitative Clinical Laboratory Results: Clinical Chemistry (Intent-to-Treat Safety Analysis Set)

Table 14.3.4.3 Quantitative Clinical Laboratory Results: Coagulation (Intent-to-Treat Safety Analysis Set)

Table 14.3.4.4 Quantitative Clinical Laboratory Results: Urinalysis (Intent-to-Treat Safety Analysis Set)

Table 14.3.4.5 Shift from Baseline in Clinical Laboratory Results: Hematology (Intent-to-Treat Safety Analysis Set)

Table 14.3.4.6 Shift from Baseline in Clinical Laboratory Results: Clinical Chemistry (Intent-to-Treat Safety Analysis Set)

Table 14.3.4.7 Shift from Baseline in Clinical Laboratory Results: Coagulation (Intent-to-Treat Safety Analysis Set)

Table 14.3.4.8 Shift from Baseline in Clinical Laboratory Results: Urinalysis (Intent-to-Treat Safety Analysis Set)

Table 14.3.4.9 Subjects with Potentially Clinically Important (PCI) Laboratory Results (Intent-to-Treat Safety Analysis Set)

Table 14.3.5.1 Actual Values and Change from Baseline in Vital Signs (Intent-to-Treat Safety Analysis Set)

Table 14.3.5.2 Potentially Clinically Important Vital Signs Results (Intent-to-Treat Safety Analysis Set)

Table 14.3.6 Study Drug Exposure (Intent-to-Treat Safety Analysis Set)

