#### **PRESENTATION OF VISITS**

For outputs, visits will be represented as follows and in that order:

Long Name (default)	Short Name
Screening	Scr
Dosing Visit 1	V1
Dosing Visit 2	V2
Dosing Visit 24	V24

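### The SAP fixes laboratory baseline at Visit 1, where no coagulation or urinalysis sample is scheduled, so the coagulation change summaries and both panels' shift tables cannot be produced as written

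*SAP*

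**What the plan says.** SAP 5.8.2 sets one rule for all laboratory panels: "Baseline is denoted as Visit 1". The footnote to SAP Table 1 repeats it and adds that, where there is no Visit 1 sample, the ratio or difference alarm is not run.

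Protocol Schedule 1 has one column for Screening and one for each of Visits 1 to 24. The coagulation row reads "Coagulation (PT, aPTT, INR) ° | X | | | | | | | | X" up to Visit 8, and the urinalysis row reads "Urinalysis with microscopy ^c | X | | | | | | | | X". The seven empty cells between the two marks are Visits 1 to 7. Both rows are marked again at Visits 16 and 24. The hematology and chemistry row does carry a Visit 1 mark.

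SAP 5.8.2 asks for descriptive statistics, change from baseline and shifts for hematology, chemistry and coagulation. SAP 9.1.1 lists Table 14.3.4.7, "Shift from Baseline in Clinical Laboratory Results: Coagulation (Intent-to-Treat Safety Analysis Set"), and Table 14.3.4.8, "Shift from Baseline in Clinical Laboratory Results: Urinalysis (Intent-to-Treat Safety Analysis Set").

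**The concern.** The rule points to a visit at which two of the panels are not sampled. A programmer who follows it gets empty shift tables for coagulation and urinalysis and an empty change section in the coagulation summary (Table 14.3.4.3). A programmer who fills them has departed from the written definition. SAP 6.2 declares only one change from the protocol's planned analyses, the dropping of clinical relief, so leaving these outputs out would be an undeclared departure.

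Coagulation is a relevant safety panel here. Protocol 1.1.2 reports five serious thrombotic events in the earlier open-label prevention study, and Protocol 5.5.2 has a stopping rule for thrombotic and thromboembolic events. With no control arm, within-subject change is the natural way to describe these parameters.

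**Working it through.** The plan gives no figure to reproduce. The check sets the baseline rule against the sampling schedule and counts what can be computed.

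**1. Sampled visits (Protocol Schedule 1; 25 cells per row, Screening plus Visits 1 to 24)**

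| Panel | Screening | Visit 1 | Visits 8, 16, 24 |
|---|---|---|---|
| Hematology and chemistry | yes | yes | yes |
| Coagulation | yes | no | yes |
| Urinalysis | yes | no | yes |

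The physical-exam, body-weight, pregnancy-test and immunogenicity rows also resolve to 25 cells, so the blank at Visit 1 is not an alignment error.

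**2. Does Visit 1 include Screening?** SAP Appendix II says "For outputs, visits will be represented as follows and in that order" and then lists Screening (Scr) and Dosing Visit 1 (V1) as separate visits. Nothing in the SAP maps a Screening sample to Visit 1.

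**3. Is there a fallback?**
- The Table 1 footnote only switches off the baseline-relative alarms; it supplies no substitute value.
- SAP 7.1 imputes missing AE severity and causality and, by its own terms, no other missing data.
- SAP 5.1 keeps unscheduled data out of the analysis unless otherwise specified.

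**4. Subject-by-visit pairs for 6 completers (SAP 3.2), at Visits 8, 16 and 24**

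Pairs = 6 × 3 = 18 where a baseline exists, otherwise 0.

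| Panel | Baseline = Visit 1 | Baseline = last scheduled pre-dose value |
|---|---|---|
| Hematology and chemistry | 18 (Screening and Visit 1 on separate days) | 18 |
| Coagulation | 0 | 18 |
| Urinalysis | 0 | 18 |

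Coagulation has three parameters (PT, aPTT, INR), so change values = 18 × 3 = 54. Under the Visit 1 rule 0 of 54 are available; under the last pre-dose rule 54 of 54 are, if every scheduled sample is taken.

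**5. Tables affected.** Of the four shift tables (14.3.4.5 to 14.3.4.8), two cannot be filled: 14.3.4.7 and 14.3.4.8.

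**6. Potentially clinically important (PCI) criteria.** SAP Table 1 has 20 test items. Three (hemoglobin, BUN, creatinine) have only baseline-relative criteria; the other 17 have fixed limits, including aPTT above 90.0 sec and PT-INR above 2.875. No urinalysis item appears. PCI items lost through the Schedule 1 gap: 0 of 20.

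**7. Screening and Dosing Visit 1 on the same day.** Protocol 6 allows this and, "to prevent repetition of protocol procedures and avoid duplicate blood draws on the same day", lists the only Visit 1 procedures still to be done. No safety laboratory panel is among them. The SAP does not say whether that day's Screening sample counts as Visit 1.
- If it does not count, the subject also has no hematology or chemistry baseline and loses 3 of 20 PCI items.
- If it does count, 0 of 20 are lost, and the subject supplies 3 parameters × 3 visits = 9 of the 54 coagulation change values.

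The documents do not give the number of such subjects; it may be zero.

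**The case against.** The best reply is that the practical risk is small. Screening is the only scheduled pre-dose sample for these two panels, so a programmer has one sensible choice and little room for a data-driven one. That is fair, and the argument from data-driven choice carries little weight. It does not repair the rule, because using Screening contradicts the definition in the text.

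A second reply is that a same-day Screening sample would naturally serve as Visit 1, so the count of zero is not absolute. This also stands: 0 of 54 is a count by visit label and would rise by 9 for each same-day subject if that sample were accepted. The SAP does not say that it is.

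Third, Protocol 9.1.5 concerns the investigator's follow-up of abnormal "values which were not present at the pre-treatment value observed closest to the start of study treatment"; it does not define a baseline for summary tables. Agreed. It shows that the closest pre-treatment value is already the protocol's reference for judging laboratory abnormalities, but it does not by itself contradict the SAP.

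Finally, every change can be read from the listings, and no inference or stopping rule is shown to depend on these tables. That limits the severity, but the planned outputs still cannot be produced as specified.

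**Conclusion.** The point holds. A stated rule, followed literally, leaves two planned safety tables and the change part of a third with no evaluable subject: 0 of 54 coagulation change values and 2 of 4 shift tables, for 6 completers with all scheduled samples taken and no same-day Screening sample counted as Visit 1. The same-day question is secondary and conditional, at 0 or 3 of 20 PCI items per such subject. Observed-value summaries, out-of-range flags, listings, fixed PCI limits and efficacy results are untouched. It should be fixed, but it threatens no conclusion of the trial.

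**What to change.** In SAP 5.8.2 and the Table 1 footnote, replace the Visit 1 definition with: *Baseline for each parameter is the last non-missing value (Screening or Visit 1) before the first CINRYZE infusion.* Apply it to the change, shift and PCI tables. It also settles the same-day case and agrees with the reference value in Protocol 9.1.5.

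The cost is one sentence and a standard derivation, with no new data. Coagulation and urinalysis baselines may then be up to 21 days before dosing (Schedule 1, footnote a), while most hematology and chemistry baselines stay at Visit 1. The table footnotes should therefore state the source visit.
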